- p All AEs and SAEs, regardless of relationship, concomitant medications, and concomitant surgical procedures will be collected from the time the subject signs the informed consent.
- q Subjects should be randomized following confirmation of eligibility on Day 1. Confirmation of eligibility on Day 1 requires a review of the Day -1 results and pre-dose Day 1 results of physical exam, AE, conmeds, vital signs and pulse oximetry. A subject is considered enrolled into the study when he or she has been randomized.
- r The Day 1 pre-dose ECG and spirometry must be reviewed before the first dose may be administered. The administration of IP should optimally occur within 2-3 hours after subjects have completed their routine pulmonary therapies (airway clearance and pulmonary medications) for the day. For subjects whose pulmonary medications do not include an inhaled short-acting beta-agonist (or it is not given within the 2 to 3 hour window prior to IP administration),

albuterol (2 to 4 puffs) will be administered approximately 20 minutes before treatment with IP. IP will be administered by the respiratory route using an InnoSpire Go nebulizer. Depending on the dose level, nebulization times will range from approximately 44 to 133 minutes (represents actual nebulization times, and does not include the rest periods between nebulizer changes). During nebulization of IP, the subject should be monitored closely for any signs or symptoms of respiratory distress (eg, dyspnea, wheezing, bronchospasm)

- s Subjects will be in a fasted state (8hrs without food or drink except water) for serum chemistry blood collections.

Table 2: Part A - Schedule of Procedures for the Follow-up Period - Day 3 to Day 85

Study Week	Follow-up Period											
	Week 1 (cont'd)	Week 2 ^a		Week 3 ^a		Week 4	Week 5	Week 7	Week 9	Week 11	Week 13	
Study Day	Day 3	Day 5	Day 8 (±1 day)	Day 11 (+3 or +4 days post Day 8)	Day 15 (±1 day)	Day 18 (+3 or +4 days post Day 15)	Day 22 (±2 days)	Day 29 (±2 days)	Day 43 (±3 days)	Day 57 (±3 days)	Day 71 (±3 days)	Day 85 (±3 days)
Clinic visit (outpatient) ^b	X		X		X			X		X		X
Telephone contact		X		X		X	X		X		X	
Physical examination	X		X		X			X		X		X
Vital signs ^c												
• Blood pressure, pulse rate, body temperature	X		X		X			X		X		X
• Respiratory rate	X		X		X			X		X		X
Pulse oximetry	X		X		X			X		X		X
Weight			X		X			X		X		X
Electrocardiogram (ECG)			X		X			X		X		X
Serum chemistry ^h , hematology, coagulation, urinalysis, CRP			X		X			X				X

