^c Approximate nebulization time is based on a flow rate of 0.3 mL/minute for the InnoSpire Go nebulizer. This represents actual nebulization time and does not include the rest periods between nebulizer changes.

^d The medication cup of the InnoSpire Go nebulizer holds a maximum of 8 mL of solution. As nebulizers will not be refilled during nebulization, multiple nebulizers, as shown in the table, will be used to deliver the specified volume for each of the dose levels of MRT5005. The MRT5005 suspension will be divided equally among the nebulizers.

Sterile normal saline (Sodium Chloride Inhalation Solution, USP 0.9%) will be used as placebo. To maintain the blind of the study, the volume and nebulization time of placebo, and number of nebulizers used to deliver placebo will match that of the MRT5005 dosing group. Normal saline should be stored (see Section [6.3.2](#)) and administered at room temperature.

For the purposes of this study, the mouthpiece of the nebulizer, which includes the medication cup and filter attachment with its filter, will be considered single-use and will not be reused for another administration. Nebulizer handles will not be reused for single dosing of subjects in Part A. However, nebulizer handles will be reused for multiple dosing in Parts B and D. In this case, nebulizer handles will be assigned to and used by only one subject.

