6.2.2.1. Dosing of IP

The administration of IP will be performed by a blinded, qualified member of the study staff. For scheduling of IP administration with respect to the subjects' routine pulmonary medications and therapies, refer to Section [5.1.1.1](#).

For administration of the IP, the subject should be seated comfortably in a chair and the nebulizer should be held in an upright position; the arm holding the nebulizer may be supported according to the subject's preference (eg, resting the elbow on the arm of a phlebotomy chair). The subject will be instructed to place the mouthpiece of the nebulizer between their teeth, with their lips firmly sealed around the mouthpiece, and to breathe through their mouth at their normal rate and tidal volume until the aerosol formation completely stops (see instruction manual for InnoSpire Go micropump nebulizer in [Appendix 3](#)). The subject should turn off the nebulizer when taking the mouthpiece out of their mouth (eg, to talk) to avoid loss of IP and to minimize secondary exposure (see below). As described above, multiple nebulizers may be used to deliver IP ([Table 11](#)); to reduce the burden of administration, the subject will be offered a 15 to 20-minute rest period before changing to the next nebulizer (if applicable; this interval may be extended if needed for subject tolerability). For example, subjects receiving the 16 mg dose level may have rest periods after the first, second, and third nebulizers for a total of 3 rest periods during the nebulization.

During nebulization of IP, the subject will be monitored closely for any signs or symptoms of respiratory distress (eg, dyspnea, wheezing, bronchospasm). In Part A and Part B, blood pressure, pulse rate, and oxygen saturation measured by pulse oximetry will be continuously monitored during nebulization (except during rest periods) and will be recorded at the end of the nebulization with each of the multiple nebulizers used to deliver the total volume of IP (eg, for the 16 mg dose, values will be recorded at the end of the nebulization with each of the 4 nebulizers used to deliver the 28 mL of total volume); the final recording will count as the Hour 0 time point. Blood pressure, pulse rate, and/or oxygen saturation may be recorded more frequently, if clinically indicated. Body temperature will not be monitored during the dosing period.

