Prior to IP administration, subjects should undergo their routine pulmonary therapies (airway clearance and pulmonary medications). These may be administered either at home or at the study center and may include but are not limited to chest physiotherapy, and treatment with inhaled bronchodilators, hypertonic saline, antibiotics, and steroids (Section [5.1.1](#)). The administration of IP should optimally occur within 2 to 3 hours after subjects have completed their pulmonary therapies for the day. For subjects whose routine pulmonary medications do not include an inhaled short-acting beta-agonist (or it is not given within the 2 to 3 hour window prior to IP administration), albuterol (2 to 4 puffs) will be administered via metered-dose inhaler approximately 20 minutes before treatment with IP to minimize any potential bronchoconstrictive effects (Section [5.1.1](#)). Note that administration of a short-acting beta-agonist via nebulization is also permitted at the discretion of the Investigator

Following confirmation of eligibility, subjects will be randomized to receive the first dose of either MRT5005 or placebo (subjects who are randomized are considered enrolled into the study). The administration of IP will be performed by a blinded, qualified member of the study staff. IP will be administered by the respiratory route using an InnoSpire Go nebulizer.

Nebulization time is expected to be approximately 22 minutes or less. See Section [6.2.2](#) for details on the preparation and dosing of IP, which includes minimizing secondary exposure to study staff during nebulization of IP.

The second through fifth doses of IP will be administered on Days 2, 3, 4, and 5, respectively. Pre-dose assessments will occur on each dosing day (as noted in [Table 8](#)) and IP should continue to be administered within 2 to 3 hours after subjects have completed their routine pulmonary therapies.

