Treatment-emergent febrile reactions and hypersensitivity reactions will be presented as a count of febrile reactions, febrile reactions by severity, hypersensitivity reactions, and hypersensitivity reactions by severity. Additionally, the table will reflect the count and percentage of subjects experiencing the following: any febrile reaction, any febrile reaction by severity, any hypersensitivity reaction, and any hypersensitivity reaction by severity. The summary will be for all subjects in the safety analysis set by dose group for each study part. In addition, the summary of treatment-emergent febrile reactions and hypersensitivity reactions will be presented for all subjects in the safety analysis set for the study overall by pooled treatment group. Febrile reactions will be identified based on a preferred term of body temperature increased or preferred term of pyrexia within the 24 hours after completion of

nebulization on any dosing day with at least one other systemic symptom reported as a preferred term of headache, arthralgia, myalgia, fatigue, chills, nausea, or vomiting within the 24 hours after completion of nebulization on any dosing day. Severity grade for febrile reactions will be based on the maximum severity of the preferred terms comprising the febrile reaction. Hypersensitivity reactions will be identified based on a preferred term of hypersensitivity within the 24 hours after completion of nebulization on any dosing day.

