Adverse events leading to withdrawal from treatment, AEs resulting in death, pulmonary exacerbations (investigator and protocol-defined), adverse events of special interest, and SAEs will be presented in data listings for subjects in the safety analysis set. Adverse events of pyrexia or body temperature increased during nebulization or within the 24 hours after completion of nebulization on any dosing day will also be listed for subjects in the safety analysis set. This listing will include all adverse events that occurred during nebulization or within the 24 hours after completion of nebulization for subjects that had an adverse event of pyrexia or body temperature increased during nebulization or within the 24 hours after completion of nebulization on any dosing day. All adverse events that occurred during nebulization or within the 24 hours after completion of nebulization will also be listed for subjects in the safety analysis set. Febrile reactions and hypersensitivity reactions within the 24 hours after completion of nebulization on any dosing day will also be listed for subjects in the safety analysis set. This listing will include all adverse events that meet the specified febrile reaction or hypersensitivity criteria that occurred within the 24 hours after completion of nebulization for subjects that had a febrile reaction or hypersensitivity reaction within the 24 hours after completion of nebulization on any dosing day.

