AE	Definition	AE_F17a	Note:	Febrile reactions were identified based on a preferred term of body temperature increased or preferred term of pyrexia within the 24 hours after completion of nebulization on any dosing day with at least one other systemic symptom reported as a preferred term of headache, arthralgia, myalgia, fatigue, chills, nausea, or vomiting within the 24 hours after completion of nebulization on any dosing day.
AE	Definition	AE_F17b	Note:	Hypersensitivity reactions were identified based on a preferred term of hypersensitivity within the 24 hours after completion of nebulization on any dosing day.
AE	Definition	AE_F17c	[2]	Severity grade for each febrile reaction was based on the maximum severity of the preferred terms comprising the febrile reaction. Febrile reactions with missing severity were counted as Severe.

Data Type	Footnote Type	Code	Prefix	Footnote
AE	Interval	AE_F18	Note:	The 1 month post-dose time interval is defined as through Day 29 for Part A, through Day 57 for Part B, through Day 32 for Part D.
AE	Count	AE_F19	Note:	N represents the number of subjects in a given dose group that experienced an adverse event.
EG	Baseline	EG_F01	Note:	The baseline value was defined as the Day -1 ECG measurement.
EG	Baseline	EG_F01D	Note:	The baseline value was defined as the screening ECG measurement.
EG	Schedule	EG_F02	Note:	Only ECGs scheduled per the protocol were summarized.
EX	Count	EX_F01	Note:	Full dose refers to completion of all nebulizers as planned; partial dose refers to incomplete nebulization. Full and partial dose are independent of the presence or absence of excess residual in the medication chamber.
VS	Schedule	VS_F01	Note:	The final recording during nebulization for blood pressure, pulse rate, and pulse oximetry was counted as the 'DAY 1 (0 HR POST-DOSE)' value.
RE	Baseline	RE_F01	[1], [3]	The baseline value was defined as the average of the results from testing on Day -1 and at pre-dose on Day 1.
RE	Baseline	RE_F01D	[1], [3]	The baseline value was defined as the result from testing pre-dose on Day 1.
RE	Baseline	RE_F01O	[1], [3]	The baseline value was defined as the average of the results from testing on Day -1 and at pre-dose on Day 1 for Part A and Part B, and defined as the result from testing pre-dose on Day 1 for Part D.
CFQ	Baseline	CFQ_F01	Note:	The baseline value was defined as the Day -1 CFQ-R respiratory domain score.

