**Notes:**

- 1.) Sort by Dose Group, Subject Number, Start Date, Stop Date, System Organ Class, Preferred Term, Verbatim Term.
- 2.) Dose groups are specified in the general programming notes.
- 3.) For any subject with a febrile reaction or hypersensitivity reaction during or within 24 hours after dosing, include all other AEs that meet the criteria for febrile reaction or hypersensitivity reaction for that subject that occurred during nebulization or within 24 hours after dosing.
- 4.) Add footnote reference [1] to column 3.

Listing 16.2.8.1 (LB\_LAA\_F\_X)  
Listing of Chemistry Values  
Population: Safety Analysis Set

Part: x  
Dose Group: xxx

Subject Number	Visit	Date/Time of Assessment/ Study Day	Lab Test (units)	Result	Classification/ CS?/ Comment	Reference Range
XXXX		YYYY-MM- DD:HH:MM:SS	Albumin	XXX		
			Alkaline Phosphatase	XXX		
			ALT	XXX		
			AST	XXX		
			Blood Urea Nitrogen	XXX		
		YYYY-MM- DD:HH:MM:SS	...	XXX		
		YYYY-MM- DD:HH:MM:SS	...	XXX		
XXXX		YYYY-MM- DD:HH:MM:SS		XXX		

Etc.

CS\_01  
Note: LB\_01

Dataset Source: ADLB

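### The febrile-reaction tables start counting only when nebulization ends, so they may under-count more at higher doses, and their source listing carries a note that contradicts them

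*SAP*

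**What the plan says.** SAP 9.4 builds the febrile reaction from two parts: a fever term (pyrexia or body temperature increased) and at least one listed systemic symptom. Both parts carry the same window. For the symptoms, the list ends "fatigue, chills, nausea, or vomiting within the 24 hours after completion of nebulization on any dosing day". Footnote AE_F17a repeats the rule under Tables 14.3.2.4 and 14.3.2.5: "preferred term of pyrexia within the 24 hours after completion of nebulization on any dosing day".

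Other displays in the same SAP section open earlier. For the general listing of peri-dose events, the text is "All adverse events that occurred during nebulization or within the 24 hours after completion of nebulization will also be listed", and the pyrexia listing (16.2.7.7) is described in the same way.

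Listing 16.2.7.9 is the named source for both febrile-reaction tables. Its programming note 3 begins "For any subject with a febrile reaction or hypersensitivity reaction during or within 24 hours after dosing", but its footnote AE_L08 and its description in SAP 9.4 cover only the time after completion.

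Dosing length depends on dose. The footnotes to Protocol Table 1 say "nebulization times will range from approximately 44 to 133 minutes (represents actual nebulization times", rests excluded. For Part D, Protocol 7.3.2 says "Nebulization time is expected to be approximately 22 minutes or less". Between nebulizers, Protocol 6.2.2.1 says "the subject will be offered a 15 to 20-minute rest period before changing to the next nebulizer", and it allows that interval to be lengthened for tolerability.

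**The concern.** Exposure begins with the first inhalation, but the counting window opens when the last nebulizer finishes. The interval in between is longest at the highest doses. Consider a 24 mg subject who has chills from the fifth nebulizer and a fever half an hour after dosing ends. If start time decides, that subject is not a febrile reaction in the tables unless another listed symptom begins after dosing.

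This touches a central safety question. The Protocol added the 20 mg single-dose group after febrile reactions at 24 mg, and added Part D to learn whether these reactions depend on dose. A counting rule whose blind interval lengthens with dose is awkward for that comparison. Separately, a programmer who follows note 3 of Listing 16.2.7.9 and one who follows AE_F17a could produce different counts from the same data.

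**Working it through.** **Inputs.** Protocol Table 11 gives nebulization minutes and number of nebulizers by dose. Its footnote gives the basis: "Approximate nebulization time is based on a flow rate of 0.3 mL/minute for the InnoSpire Go nebulizer". Concentration is 0.6 mg/mL (Protocol 6.2.2). Rests are 15 to 20 minutes, one fewer than the number of nebulizers (Protocol 6.2.2.1). Active subjects per group are 3 in Parts A and B and 6 in Part D (SAP 2.5).

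**1. Reproduce the plan's times.** Dose / 0.6 mg/mL / 0.3 mL/min gives 22.2, 44.4, 66.7, 88.9, 111.1 and 133.3 minutes for 4, 8, 12, 16, 20 and 24 mg. Table 11 states 22, 44, 66, 89, 110 and 133. They agree; the largest difference is 1.1 minutes.

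**2. Elapsed time from first inhalation to the opening of the window.** Elapsed = Table 11 minutes + (nebulizers - 1) x rest.

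| Dose | Nebulizers | No rests | 15 min rests | 20 min rests |
|---|---|---|---|---|
| 4 mg | 1 | 22 | 22 | 22 |
| 8 mg | 2 | 44 | 59 | 64 |
| 12 mg | 3 | 66 | 96 | 106 |
| 16 mg | 4 | 89 | 134 | 149 |
| 20 mg | 5 | 110 | 170 | 190 |
| 24 mg | 6 | 133 | 208 | 233 |

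At 24 mg: 133 + 5 x 15 = 208 and 133 + 5 x 20 = 233 minutes, or 3.5 to 3.9 hours. That is about 10 times the 4 mg figure (208/22 = 9.5; 233/22 = 10.6). With no rests it is 133/22 = 6 times.

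**3. Where the window lies.** Measured from first inhalation, it runs from 0.4 to 24.4 hours at 4 mg and, with 20-minute rests, from 3.9 to 27.9 hours at 24 mg. It lasts 24 hours at every dose but sits later at higher doses. In Part D, if dosing is at the same clock time each day, Days 2 to 5 dosing (24.0 to 24.4 hours after the previous start) lies inside the previous day's window, so essentially only the 22 minutes on Day 1 are uncovered.

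**4. Which part is exposed.** Protocol 6.2.2.1 says temperature is not monitored during dosing, so a fever onset is unlikely to be recorded then. Adverse events are collected in the dosing column of Protocol Tables 1 and 7, and SAP 9.3 treats them as treatment-emergent from the treatment start time. Chills, nausea or headache during dosing can therefore be recorded. Losing either part loses the reaction.

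**5. The specifications side by side.**

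| Place | Opens at |
|---|---|
| SAP 9.4, definition | End of nebulization |
| AE_F17a (Tables 14.3.2.4, 14.3.2.5) | End of nebulization |
| SAP 9.4, text on the febrile-reaction listing | End of nebulization |
| AE_L08 (Listing 16.2.7.9) | End of nebulization |
| Note 3 to Listing 16.2.7.9 | During nebulization |
| SAP 9.4, text on Listings 16.2.7.7 and 16.2.7.8 | During nebulization |

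The last row is a separate display choice. Note 3 is a direct conflict within one listing.

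**6. What one subject is worth.** 1/3 = 33 points in a Part A or B group; 1/6 = about 17 points in the 4 mg group. Protocol 2.2.3 reports 3 subjects with febrile reactions at 24 mg. If all were on active drug, 0, 1, 2 or 3 reclassifications would give 3/3, 2/3, 1/3 or 0/3. This is an illustration: the documents give no onset times, so the number affected cannot be computed.

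**The case against.** The other side has a good case on several points.

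- **The anchor follows the Protocol.** The stopping rules in Protocol 4.5.1 and 4.5.4 count fever in the 24 hours following administration, and the schedules set Hour 0 at the end of nebulization. The SAP window is a defensible choice. This stands.
- **Start time is not stated.** AE_F17a does not say whether a symptom must begin in the window or only be present in it. Chills that persist past Hour 0 could qualify under the second reading. This stands, and it is itself a reason to clarify. The SAP's interval footnote (AE_F15) goes by event start day, and Listing 16.2.7.7 computes start time relative to the end of nebulization, so start time is the more natural reading.
- **The events are not lost.** Table 14.3.1.2 tabulates each preferred term by dose group, with a Study Day 1 interval, and Listings 16.2.7.7 and 16.2.7.8 show events during dosing by subject. This stands, but readers will take the composite febrile-reaction rate by dose from Table 14.3.2.4.
- **A wider window has its own dose-related effect.** Time at risk would be about 24.4 hours at 4 mg and up to 27.9 hours at 24 mg (27.9/24.4, about 14% longer), and longer nebulizing may itself cause headache, fatigue or nausea. This stands and shapes the fix.

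A reader might infer that the rule flattens the dose-fever relation, or biases it toward no dose dependence. The documents do not support that. They show no onset during dosing, and the window is moved rather than shortened, so higher doses also gain later hours. Nor is 3.9 hours a maximum: it assumes five 20-minute rests, which are offered and may be extended.

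**Conclusion.** The point holds as a possible, dose-related under-count together with a definite inconsistency in the specifications. If adverse event start time governs, a qualifying term that starts during dosing falls outside Tables 14.3.2.4 and 14.3.2.5. The uncounted time grows from about 22 minutes at 4 mg to 133 minutes at 24 mg without rests, or 208 to 233 minutes with rests of 15 to 20 minutes, and longer if rests are extended. Whether any reaction is lost is unknown.

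Only Table 14.3.2.4, read across Parts A, B and D, can show a dose relation; Table 14.3.2.5 pools all active doses. The conflict between note 3 of Listing 16.2.7.9 and the SAP text with AE_F17a and AE_L08 does not depend on onset times and needs resolving in any case. This is a cheap improvement to a counting rule on an important question, not a demonstrated bias.

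**What to change.** - State in SAP 9.4 and AE_F17a that adverse event start time decides whether a term falls in the window.
- Use one window, from the start of the first nebulizer to 24 hours after completion of the last, for both the fever and the companion terms. Apply it in SAP 9.4, AE_F17a, AE_L08, Tables 14.3.2.4 and 14.3.2.5 and Listing 16.2.7.9, adjusting the display titles to match.
- Keep the after-completion count as a second row in both tables. It preserves the Protocol's anchor and lets the reader see whether the extra time at higher doses, or symptoms of nebulization itself, accounts for any difference.
- Listing 16.2.7.9 also feeds the hypersensitivity tables, whose footnote AE_F17b has the same opening point, so decide that window at the same time.

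The cost is a few lines of SAP text, the footnotes and one extra row per table. No new data are needed: start and end times are already listed for each nebulizer (SAP 7, Listing 16.2.5.3).

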7.5.2. Safety

The name and address of each third party vendor used in this study will be maintained in the Investigator's and Sponsor's files, as appropriate.

Actual safety assessment times will be monitored and recorded. The Sponsor's expectation is that the Investigator will ensure that every effort is made to perform all assessments at the protocol-scheduled time according to the suggested guidelines described in Section [7.1](#).

The Investigator can use their judgment in performing the following procedures as described in the Schedule of Procedures in [Table 1](#) through [Table 9](#).

- If a subject is experiencing respiratory distress or respiratory symptoms, based on the judgment of the Investigator, unscheduled spirometry testing may be performed when the subject is stable.
- At the Investigator's discretion, a chest x-ray may be performed at any time during the study if the subject is experiencing respiratory symptoms that warrant it.

At the discretion of the Investigator, other unscheduled procedures or tests may be performed if needed to ensure subject safety.

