**Notes:**

- 1) *Include all visits where ECGs were scheduled per the protocol.*
- 2) *Only subjects with non-missing values at baseline and the post-baseline visit are included in the denominators for the percentages.*

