**Notes:**

- 1) *Include all visits where chest x-ray was scheduled per the protocol.*
- 2) *Only subjects with non-missing values at baseline and the post-baseline visit are included in the denominators for the percentages.*

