**Notes:**

- 1) *Include all visits where physical examination was done.*
- 2) *Include all physical examination parameters*
- 3) *Only subject with non-missing values at each visit are included in the denominators for the percentages.*
- 4) *For Part D, label Screening as Baseline*

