**Notes:**

- 1) *Parameters include: FEV1, Percent Predicted FEV1, FVC, Percent Predicted FVC, FEV1/FVC, FEF25-75%, PEF*
- 2) *Include all planned (per the protocol) post-baseline visits/timepoints where spirometry is performed and collected.*

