CFQ	Baseline	CFQCH_F01	Note:	At baseline, all subjects with baseline data contributed to the reported baseline mean. For each visit, the mean actual value was the mean across all subjects with data at that visit. The change from baseline was calculated for each subject with data at baseline and that visit, then reported as a mean change.
XR	Schedule	XR_F01	Note:	Only chest x-rays scheduled per the protocol were summarized.

Translate Bio, Inc.  
PROTOCOL NUMBER MRT5005-101

A Phase 1/2, Randomized, Double-Blind, Placebo-Controlled, Combined Single and Multiple Ascending Dose Study Evaluating the Safety, Tolerability, and Biological Activity of MRT5005 (████████ mRNA/████ LNP) Administered by Nebulization to Adult with ████████ic Fibrosis

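### Symptom-driven chest x-rays and spirometry are left out of the shift and change tables for two primary-endpoint components

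*SAP*

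**What the plan says.** The primary endpoint (Protocol 2.4.1, SAP 2.2.1) combines treatment-emergent adverse events, including pulmonary exacerbations, with changes from baseline in a list of measures that includes chest x-ray and spirometry. Spirometry is also the secondary endpoint.

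Protocol 7.5.2 allows extra testing. Films are left to the judgement of the site: "a chest x-ray may be performed at any time during the study if the subject is experiencing respiratory symptoms that warrant it". For respiratory distress or symptoms, "unscheduled spirometry testing may be performed when the subject is stable". Footnote o of Protocol Table 4 repeats the x-ray allowance for the Part B treatment period.

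The SAP table specifications then limit what is tabulated:

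- **Table 14.3.7.1 (x-ray shifts):** note 1 says "Include all visits where chest x-ray was scheduled per the protocol", and footnote XR_F01 says "Only chest x-rays scheduled per the protocol were summarized".
- **Table 14.3.9.1 (spirometry, absolute change):** note 2 says "Include all planned (per the protocol) post-baseline visits/timepoints where spirometry is performed and collected". Table 14.3.9.2 (relative change) repeats this table and inherits the limit.

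The limit is not in the SAP body. Sections 9.6.3.2 and 9.6.3.3 refer to post-baseline visits without restricting them to scheduled tests. Other safety tables are wider: for physical examination (Table 14.3.8.1) the note is "Include all visits where physical examination was done", and the vital-sign and laboratory notes refer to visits at which data are collected.

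**The concern.** A test ordered because a subject has respiratory symptoms is more likely to be abnormal than a routine one. Leaving such tests out is therefore not a neutral loss of data, because whether a result is tabulated depends on why the test was done. The product is inhaled and first-in-human, and the lung is where the protocol expects any adverse effect (2.2.3). If a symptom-driven film shows a new abnormality and the next scheduled film is clear, the shift table shows no shift for that subject. The same can happen to a fall in ppFEV1 that recovers before the next planned test. A reader who relies on the tables for these two components would not see either event there.

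**Working it through.** The plan gives no figure to reproduce. The check sets the schedule against the table rules.

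**1. Chest x-ray (Protocol 7.5.2.13).** Scheduled post-dose films are Days 8 and 29 (Part A), 36 and 57 (Part B), and 11 and 32 (Part D). Days from first dose to first scheduled film:

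- Part A: 8 − 1 = 7
- Part B: 36 − 1 = 35
- Part D: 11 − 1 = 10

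Part B doses fall on Days 1, 8, 15, 22 and 29. The first scheduled film comes 36 − 29 = 7 days after the last dose. Any film taken during the five-dose period is therefore unscheduled and is excluded from Table 14.3.7.1 by XR_F01, although Table 4 footnote o foresees such films.

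**2. Spirometry (Protocol Tables 1 to 9).** Counting scheduled tests after the first dose gives 11 in Part A, 23 in Part B and 12 in Part D. The longest gaps are 169 − 85 = 84 days (A), 197 − 113 = 84 days (B) and 341 − 229 = 112 days (D). Coverage during dosing is dense, so the exclusion matters less here than for films.

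A gap remains in Part D. Spirometry is scheduled on Days 1 to 5 and next on Day 11, with only a telephone contact on Day 8. A fall first seen at the Day 5 pre-dose test and checked again before Day 11 would be checked by an unscheduled test, which Tables 14.3.9.1 and 14.3.9.2 omit.

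**3. Other places where the result could appear.**

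- **Tables:** SAP Section 14 plans no worst post-baseline or any-time table for either measure.
- **Listings:** 16.2.11.1 (x-ray) and 16.2.13.1 (spirometry) state no scheduled-only limit.
- **Adverse events:** Protocol 8.1.4 lets a clinically relevant change be an adverse event if the investigator judges it so.
- **Exacerbations:** Protocol 8.1.7 requires a new or changed antibiotic plus at least 4 of 12 signs. Radiographic change and a 10% fall in pulmonary function are two of the 12. An isolated FEV1 fall does not qualify as protocol-defined, though physician-reported exacerbations are also recorded.
- **Figures:** the notes to the individual ppFEV1 plot (14.3.9.1.2) include all post-baseline visits, but its stated source is the planned-visit table. Whether unscheduled tests are plotted is unclear.

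**4. Weight of one subject.** Active groups have 3 subjects in Parts A and B (1/3 = 33%) and 6 in Part D (1/6 = 17%). As an assumed illustration, suppose one Part B active subject has a clinically significant film in Week 3, and the Day 36 and Day 57 films have returned to baseline. Table 14.3.7.1 as specified shows 0 of 3 with a shift. An any-time row shows 1 of 3.

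**The case against.** The strongest reply is that the information is not lost. Treatment-emergent adverse events and both types of exacerbation are part of the same endpoint and are tabulated by dose group, so a clinically relevant finding can reach a summary that way. The listings carry the values, and Protocol 9.8.1 promises only that clinically important findings will be summarized or listed. Groups are small enough to read subject by subject. Safety decisions do not rest on these tables either: for the study stopping criteria, the safety committee reviews all available safety data (Protocol 4.5.6). Finally, a lowest-value row has its own bias, since a minimum over some 23 tests falls by chance without any drug effect.

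Most of this stands, and it rules out three stronger readings that a reader might infer:

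- **That these results never reach a summary of the primary endpoint.** The adverse-event and exacerbation tables are such summaries.
- **That the exclusion always favours no change.** This is not shown. Unscheduled spirometry is done once the subject is stable, not necessarily at the lowest point, and an unscheduled film may be normal.
- **That the long stretch without scheduled films after Day 29, 57 or 32 measures the problem.** It describes the protocol's schedule, not the number of films excluded. The shift table has no row for that time and makes no statement about it.

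ECG is a weaker case. Its table has the same limit ("Only ECGs scheduled per the protocol were summarized"), but the protocol has no symptom-driven ECG provision, only a general allowance for other unscheduled tests.

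The reply does not remove the point. The adverse-event route depends on investigator judgement, the protocol-defined exacerbation route needs several criteria together, and neither shows change from baseline in the measure itself.

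**Conclusion.** The concern holds as a reporting gap of modest size, limited to chest x-ray and spirometry. By stated rule, symptom-driven results are outside the shift and change tables for two named primary-endpoint components. They are visible only in listings, or indirectly through adverse events or exacerbations. The firmest instance is Part B, where no film from the dosing period can enter Table 14.3.7.1. The number of results affected cannot be derived from the documents. The conclusion assumes that some symptom-driven tests were done, as the protocol foresees, and that the shells will be programmed as written.

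**What to change.** Keep the by-visit rows on scheduled visits and make these additions:

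- **Table 14.3.7.1:** a shift row for the worst post-baseline result, scheduled or unscheduled.
- **Tables 14.3.9.1 and 14.3.9.2:** a row for the lowest post-baseline ppFEV1, scheduled or unscheduled, with its absolute or relative change from baseline.
- **All three tables:** the row for each dose group and for placebo (pooled in Parts A and B), so that the chance fall in a minimum can be seen in the controls. A footnote should give the total number of tests per subject, scheduled and unscheduled.
- **Wording:** amend XR_F01 and note 2 of Table 14.3.9.1 to match. An equivalent ECG row, with EG_F02 amended, is optional.

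The cost is shell wording and one derived record per parameter per subject, from data already collected. The remaining drawback is that subjects tested more often have more chances of a low value. The placebo row and the test counts make this visible but do not remove it.
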